4.6 Outcomes

Clinical timings

Members of the study team will be present during simulations and will manually record this at the simulated out-of-hospital cardiac arrest site, and confirm the timings following analysis of video recordings:

- Total time from 999-call to AED application (and to first shock).
- Time away from the patient's side.
- Hands off CPR time.

Hands-off CPR time is the time between stopping chest compressions and recommencing chest compressions when attaching and using an AED. 'Time away from patient's side' allows us to quantify the *additional* hands-off CPR time caused by leaving the patient to retrieve the AED that the drone has delivered nearby.

Drone timings

The study team will record these following analysis of 999 call audio and drone-mounted video, supplemented by manual recordings by the study team at the simulated out-of-hospital cardiac arrest site:

- Time from 999-call to 'ready for flight' and 'start of flight' (following Guardian UTM approvals).
- Total flight time.
- Time from arrival on scene to AED safe to retrieve and to AED attached to patient.

Additional information

We will collect participant feedback immediately following the end of the simulation, using the approach from our previous simulation study (19):

- Questionnaire, based on the 'System Usability Scale', developed to evaluate usability of new devices or systems (44) (**appendix 2**).
- Brief (\leq 5 minute) conversation. We will ask about age, gender and previous CPR/defibrillator training and real-world experience. We will ask them their thoughts about the simulation, using a style from resuscitation courses evaluating behaviours during mock cardiac arrests (45) (**appendix 3**).

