In eight single-bystander simulations in Sweden, the hands-off CPR time (the time from stopping CPR to retrieve the AED to the time that CPR commences again once the AED has been attached and delivered a shock) was a mean of 94 seconds (range 75-110 seconds) (17).

Our research team has existing experience of carrying AEDs by drone, demonstrating the use of fixed-wing aircraft to carry an AED a total of 92km over six test flights in a coastal air corridor in Wales. The AED was dropped by parachute from 120m, and landed within 50m of the target location (20).

We have subsequently developed a delivery system using a rotary-wing drone, demonstrating that we could carry an AED and safely lower it via winch at the exact location required (<5m) in simulated out-of-hospital cardiac arrests (19). Notably, the Stockholm team use a winch mechanism for their live operations (15, 16).

In our latter study (19), participants made a simulated 999-call, performed CPR and were instructed that an AED would arrive via drone. Participants felt uncomfortable leaving the patient's side and asked the 999-call-handler for permission to leave the patient - even though they had heard the AED's arrival and an audible siren indicating it was safe to approach. They appreciated that the cognitive burden of deciding whether or not to try and retrieve a distant AED had been removed from them. Hands-off CPR time was a median 109 seconds (interquartile range 87-130 seconds) in 18 simulations. However, only 19 seconds of this hands-off time was time actually away from the patient's side: only a small addition to hands-off CPR time compared to a situation where an AED is placed directly in their hands by someone else. Drone-

delivery of AEDs may therefore be appropriate for situations where there is only one bystander.

In the UK, 'Beyond Visual Line of Sight' (BVLOS) drone flights are generally limited by the CAA to research studies in pre-agreed flight corridors. However, within these corridors there are opportunities to test drone carriage of AEDs.

We are ready to demonstrate an optimised, fully-integrated drone-delivery system (from 999-call to AED attached to patient) to the CAA and to the public. This will put ambulance services across the UK in a position where they can test and implement drone-delivery AEDs as soon as possible.

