4.3 Approach and rationale

Demonstrate an AED drone-delivery system that is fully integrated with ambulance service systems, in 'end-to-end' BVLOS flights for simulated out-of-hospital cardiac arrests.

We have previously demonstrated that study participants can interact with a drone-delivered AED (19). What has not been tested before in the UK is a fully-integrated system that allows the BVLOS delivery of an AED via drone following diagnosis of cardiac arrest during a 999 call.

In this work package, we will ask study participants to come to the aid of simulated out-of-hospital cardiac arrest patients and to call '999'. The call will be directed to a WAST training call centre, which operates in the same way as a real 999 call, and used by us in our previous simulation study (19). In all other regards, the processes demonstrated in this work package (cardiac arrest diagnosis, automated drone activation, drone flight, real-time communications between drone and Emergency Operations Centre, AED delivery) will occur as they would in a real-world scenario.

When delivering an AED via drone, one important consideration is how long it takes a bystander to retrieve and attach the AED. Unnecessary delays in performing CPR can be detrimental to patient outcome, but potential delays caused by retrieving and using an AED must be balanced against the potential benefits of early defibrillation. Not all

patients in cardiac arrest will be suitable for defibrillation. It is not possible to know this in advance – an AED performs heart rhythm analysis and then shocks / does not shock according to its findings. Knowing how quickly a shock can be delivered and how long a bystander has to spend away from a patient to retrieve an AED will be an important consideration when implementing effective drone-delivered AED systems in the future.

Our previous simulation study demonstrated the importance of the bystander / 999 call-handler interaction in the process of retrieving and using a drone-delivered AED. This study will use information from audio/video analyses and from conversations to help ambulance services determine how best to communicate information about the arriving drone, and how best to offer advice during the 999 call about using an AED effectively.

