4.4 Study design

This will be an end-to-end test of drone-delivery of AEDs for simulated out-of-hospital cardiac arrest.

A study participant will find an adult ‘patient’ (a resuscitation manikin) in an outdoor location. They will be instructed only that: the person has collapsed in front of them and is not breathing and that they should call ‘999’. We will provide participants with a mobile phone with a pre-programmed number to make this call. The 999 call will connect to a WAST call-handler at a training centre.

The call-handler will handle it as a real-world call, asking questions, diagnosing cardiac arrest and providing telephone CPR instructions according to existing protocols. Once

cardiac arrest has been diagnosed during the 999 call, an automated instruction will be sent to a remote-located drone. This will start up, determine an appropriate flight-path and fly an AED to the cardiac arrest location. The drone pilot and 999 call-handler will have a 'live' line of communication during the flight.

The call-handler will inform participants that they have dispatched an AED via drone and update them when the drone's arrival is imminent. The drone will hover at the target location and lower the AED to the ground via winch. Video-recording equipment is integral to the drone and the drone operator can review in real-time that it is safe and appropriate to lower the AED to the ground. The winch will retract and the drone will hover above the AED to help indicate its location. The drone operator will indicate to the call-handler that it is safe to approach the drone, and the call-handler will relay this information to the participant. Once the participant has retrieved the AED the drone will start its flight back to its start location. The participant will then attach the AED to the patient. The AED will prompt them to deliver a single shock to the patient and the scenario will end.

The drone system will integrate with a commercial Unified Traffic Management (UTM) system (Guardian UTM) to simulate delays caused by receiving necessary BVLOS permission from the Civil Aviation Authority that would occur in unrestricted real-world flights outside of the designated corridor used for this study.

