4.7 Analyses

We will report timings and score from the questionnaire based on the System Usability Scale using median and interquartile range.

The study team will review other data collected during the study itself:

- Audio recordings of 999-calls and voice/text interactions between drone pilot and 999 call-handler.
- Video from the drone itself during flight.
- Video from the scene of participant interaction with drone and AED.

- Feedback from 999-call-handler and drone operator.
- Real-time observations and field-notes about the out-of-hospital cardiac arrest simulations.

We will review participant feedback and on-site observations after each flight session to identify any critical issues before subsequent sessions. We will collate the summated information following the simulation to identify key themes related to: drone activation process, real-time in-flight communications between drone and ambulance service, and interaction between bystander and drone. Our aim is to iteratively improve the integrated drone-dispatch process throughout the study period, and in preparation for future flight operations for real-life out-of-hospital cardiac arrests.

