4.8 Ethical and safety considerations

We are conducting simulated cardiac arrest scenarios, but this may be a sensitive topic for some bystanders (for example, if they have real-life experience of finding a collapsed casualty). The Participant Information Sheet includes information about sources of help for any participant who experiences distress. Our PPI representatives have reviewed this information.

During the simulation itself a participant can stop at any time if they experience distress, and a member of the research team will be immediately on hand to stop the simulation or provide support if required.

We will keep a record of any adverse events of which we become aware. If there are any Serious Adverse Events related to the simulation, then we will inform the sponsor within 24 hours of us becoming aware. Should this happen, we will approach the Warwick CTU Quality Assurance team for the appropriate template to submit the report.

Drone flight will take place in a pre-determined flight corridor and be subject to approval from the CAA, following the submission and approval of a detailed Operating Safety Case. The development work allows for 45 days of flying and development work

before the start of this work package – this has been fully costed and resources and time have been appropriately allocated for this.

The Guardian UTM system deconflicts our drone flight with manned and unmanned traffic, by redirecting or grounding other aircrafts or by rejecting or altering the flight plan. SkyBound's automated drone station also has technology to monitor manned and unmanned aircrafts within the airspace. These technologies will automate the BVLOS permission activities required to get airborne and allow the drone to respond as quickly as possible.

Flights will be conducted by an experienced and fully-trained drone pilot employed by SkyBound. We will control access to the simulation study site so that there are no 'uninvolved' personnel present at the site where the drone will lower the AED (i.e. only study personnel and the study participant for that particular simulation will be present).

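### Hands-off CPR time ends when compressions restart (4.6), but the scenario stops at the single shock (4.4), so a run conducted as written yields only a lower bound

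*Protocol*

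**What the plan says.** Section 4.6 (Outcomes, Clinical timings) lists three timings for each simulation: time from the 999 call to AED application and first shock, time away from the patient's side, and hands-off CPR time. It defines the last of these: "Hands-off CPR time is the time between stopping chest compressions and recommencing chest compressions when attaching and using an AED". Staff record the timings by hand on site and then "confirm the timings following analysis of video recordings".

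Section 4.4 (Study design) describes the run step by step. Its last step, after the participant attaches the AED, is: "The AED will prompt them to deliver a single shock to the patient and the scenario will end".

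Section 4.8 limits who is on site: "only study personnel and the study participant for that particular simulation will be present". Section 4.7 gives the summary: "We will report timings and score from the questionnaire based on the System Usability Scale using median and interquartile range". Section 4.5 sets the sample size at 20 participants.

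Section 1.2 describes the same measure in the Swedish simulations, where the interval runs to "the time that CPR commences again once the AED has been attached and delivered a shock".

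**The concern.** The outcome needs an event that comes after the point at which the run stops. Compressions must restart for the interval to close, yet the scenario is over once the shock is delivered. The participant is the only person described as giving compressions, so nobody else in the scenario would supply the restart.

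If runs follow 4.4, the quantity reported as hands-off CPR time will be shorter than the quantity defined. If some runs stop at the shock and others carry on to a restart, 4.7 would pool truncated and complete intervals in one median and interquartile range.

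The outcome is not redundant. Section 4.3 weighs interruptions to CPR against the benefit of early defibrillation, and hands-off CPR time is the only listed timing that covers interruptions while the participant is beside the patient.

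**Working it through.** The plan gives no figure to reproduce here. The check sets the end of the outcome against the end of the scenario.

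**End points side by side**

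| Timing (4.6) | Ends at | Within the scenario of 4.4? |
|---|---|---|
| 999 call to AED application | pads attached | yes |
| 999 call to first shock | shock | yes |
| Time away from the patient's side | return to the patient | yes |
| Hands-off CPR time | first compression after AED use | no |

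**What is recorded**

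1. For each run, hands-off time = (compressions stop to shock) + (shock to restart). Call the second term g, with g ≥ 0.
2. A run that ends at the shock yields: recorded value = defined value − g.
3. Because this holds for each run, every ordered recorded value is at most the corresponding ordered true value. The recorded median and both quartiles therefore cannot exceed the true ones.
4. If all 20 runs end as 4.4 says, 0 of 20 contain the defined end event.
5. A participant might restart compressions between fetching the AED and the shock. That completes an earlier pause, but the pause around the shock is still open when the run ends, so the total remains a lower bound.

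**Size of the shortfall**

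The documents give no value for g. Purely as an assumption, take g between 5 and 20 s and set it against the 109 s median of the team's earlier 18 simulations (section 1.2):

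- 5/109 = 4.6%
- 20/109 = 18.3%

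This range only gives a sense of scale. Section 1.2 does not say where the 109 s interval ended.

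**Whether time away can stand in for it**

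Of that 109 s, section 1.2 reports that "only 19 seconds of this hands-off time was time actually away" from the patient.

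- 19/109 = 17.4% away from the patient
- 109 − 19 = 90 s, and 90/109 = 82.6% at the patient's side

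These are differences between summary figures and so approximate; section 1.2 does not say what statistic the 19 s is. They show that time away covers a small part of hands-off time. They do not measure the shortfall, which is g alone.

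**The case against.** The strongest reply is that the sentence in 4.4 is narrative and not a stopping rule. It may mean one shock cycle instead of several, with the run closing shortly afterwards. Section 4.6 is the text that governs measurement, and it names the end event, so staff who must record a restart would have to wait for one. Other text makes that plausible: the call-handler gives CPR instructions as in a real call (4.4), the AED gives voice instructions (3.2), scene video is reviewed (4.7), and the team has reported a measure of this name before (1.2).

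This reading is possible, but the protocol nowhere states it. None of the cited text says that compressions resume after the shock. Video review cannot recover an event that the scenario did not let happen, and neither can a statistical analysis plan.

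The reply is stronger on consequences, and much of that part stands. Work package 2 is descriptive, and the protocol plans no test and no formal comparison with the earlier 94 s or 109 s figures. The two quantities that 4.3 singles out, "Knowing how quickly a shock can be delivered and how long a bystander has to spend away from a patient to retrieve an AED", are both unaffected. The extra interruption caused by fetching the AED is captured by time away. Most of the hands-off interval, up to the shock, is still recorded. The count of 0 in 20 is conditional on every run ending as 4.4 says.

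**Conclusion.** The concern holds. Sections 4.4 and 4.6 cannot both be followed as written, and a run conducted under 4.4 gives only a lower bound on hands-off CPR time. The direction is certain (values too short, never too long). The size cannot be computed, because the time from shock to restart is not in the documents.

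One of the three clinical timings is affected; the other clinical timings and all drone timings are sound. The conclusion assumes that runs stop, and timing with them, at the shock. If staff in practice let participants resume compressions, the data could be complete, but the protocol would then not describe what was done.

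This should be fixed before flying starts. It does not threaten the main aims of the work package.

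**What to change.** Reconcile the two sections before the first flight day, in one of two ways:

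1. **Change 4.4.** End the scenario at the first chest compression on the manikin after the shock, and time it from the scene video that is already planned. The outcome in 4.6 then stands as defined.
2. **Change 4.6.** Redefine the outcome as time from last compression to shock, rename it accordingly, and state that it is not directly comparable with figures that run to CPR restart, such as the Swedish 94 s mean. The same caution applies to the 109 s median unless that study's end point is shown to match.

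The first option keeps the outcome as intended and adds seconds to each run. The second adds nothing to the runs but gives up the post-shock part of the interval. Either needs one sentence in the protocol and no extra staff, equipment or participants.

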4.7 Analyses

We will report timings and score from the questionnaire based on the System Usability Scale using median and interquartile range.

The study team will review other data collected during the study itself:

- Audio recordings of 999-calls and voice/text interactions between drone pilot and 999 call-handler.
- Video from the drone itself during flight.
- Video from the scene of participant interaction with drone and AED.

- Feedback from 999-call-handler and drone operator.
- Real-time observations and field-notes about the out-of-hospital cardiac arrest simulations.

We will review participant feedback and on-site observations after each flight session to identify any critical issues before subsequent sessions. We will collate the summated information following the simulation to identify key themes related to: drone activation process, real-time in-flight communications between drone and ambulance service, and interaction between bystander and drone. Our aim is to iteratively improve the integrated drone-dispatch process throughout the study period, and in preparation for future flight operations for real-life out-of-hospital cardiac arrests.

4.8 Ethical and safety considerations

We are conducting simulated cardiac arrest scenarios, but this may be a sensitive topic for some bystanders (for example, if they have real-life experience of finding a collapsed casualty). The Participant Information Sheet includes information about sources of help for any participant who experiences distress. Our PPI representatives have reviewed this information.

During the simulation itself a participant can stop at any time if they experience distress, and a member of the research team will be immediately on hand to stop the simulation or provide support if required.

We will keep a record of any adverse events of which we become aware. If there are any Serious Adverse Events related to the simulation, then we will inform the sponsor within 24 hours of us becoming aware. Should this happen, we will approach the Warwick CTU Quality Assurance team for the appropriate template to submit the report.

Drone flight will take place in a pre-determined flight corridor and be subject to approval from the CAA, following the submission and approval of a detailed Operating Safety Case. The development work allows for 45 days of flying and development work

before the start of this work package – this has been fully costed and resources and time have been appropriately allocated for this.

The Guardian UTM system deconflicts our drone flight with manned and unmanned traffic, by redirecting or grounding other aircrafts or by rejecting or altering the flight plan. SkyBound's automated drone station also has technology to monitor manned and unmanned aircrafts within the airspace. These technologies will automate the BVLOS permission activities required to get airborne and allow the drone to respond as quickly as possible.

Flights will be conducted by an experienced and fully-trained drone pilot employed by SkyBound. We will control access to the simulation study site so that there are no 'uninvolved' personnel present at the site where the drone will lower the AED (i.e. only study personnel and the study participant for that particular simulation will be present).

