Appendix 3 – Post-event conversation questions (work package 2)

PARTICIPANT NUMBER _____

Age (in years) _____

Gender (M, F, identifies another way – specify) _____

Training in last five years (Yes/No)

CPR only _____

AED only _____

Both _____

Real-world experience in last five years (Yes/No, number of occasions if yes)

CPR only _____

AED only _____

Both _____

Opening question:

- “What are your thoughts on how that went?”

Probing questions (if needed):

- “Did you encounter any difficulties in retrieving the defibrillator?”
- “Is there something that would make it easier for you to retrieve the defibrillator”

Closing question:

- “Is there something else you would like to add to your answers so far?”

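### Work package 2 records adverse events only as the team becomes aware of them and never directly asks participants about injury, discomfort or distress, so minor or undisclosed events can be missed

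*Protocol*

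**What the plan says.** Section 4.8 sets the rule for work package 2: "We will keep a record of any adverse events of which we become aware". Serious events have a reporting route that also starts from awareness: "If there are any Serious Adverse Events related to the simulation, then we will inform the sponsor within 24 hours of us becoming aware".

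The protocol expects that harm is possible. Section 4.5 names bodily or emotional distress as a reason why someone may be unable to finish the simulation. Section 4.8 recognises that the scenario may be sensitive for some participants.

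Several provisions bring events to the team's notice:

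- Section 4.8: "a member of the research team will be immediately on hand to stop the simulation or provide support if required".
- Section 4.6, on timings: "Members of the study team will be present during simulations and will manually record this".
- Section 4.7 lists the material to be reviewed. It includes 999-call audio, field-notes and "Video from the scene of participant interaction with drone and AED".
- Section 4.7 also says: "We will review participant feedback and on-site observations after each flight session to identify any critical issues before subsequent sessions".

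Both instruments given to participants after the run are printed in full. Appendix 2 has four items, on complexity, ease, confidence and whether most people could do the task. The Appendix 3 conversation opens with "What are your thoughts on how that went", has two optional probes about retrieving the AED, such as "Did you encounter any difficulties in retrieving the defibrillator", and closes by inviting anything further. Section 4.6 lists no adverse event outcome.

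**The concern.** Every participant already has a short conversation with the team straight after the run, and it is the natural place to ask about harm. It does not ask. A sore wrist from compressions on the ground, a fright as the drone came overhead, or upset that the participant keeps private may be invisible to an observer and on video, and would enter the record only if volunteered. The only specific probes point to AED retrieval.

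The protocol describes completion of this work package as one of the steps needed before testing in real cardiac arrests, so the adverse event record may be consulted later. If it is empty, a reader cannot tell whether minor events did not occur or were not mentioned, nor how many people had been asked.

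**Working it through.** **1. Is there a direct question?** Set the foreseen harms against each item put to the participant.

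| Source | Content | Asks about injury, discomfort or distress? |
|---|---|---|
| Appendix 2, items 1 to 4 | complexity, ease, confidence, others' ability | No |
| Appendix 3, opening question | general thoughts on the run | Not directly; allows a report |
| Appendix 3, two probes | difficulty and ease of retrieving the AED | No |
| Appendix 3, closing question | anything to add | Not directly; allows a report |

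No item asks directly. Two open items allow a report without prompting one.

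**2. Which events are exposed?** Visible events, such as collapse, evident upset or stopping the run, are covered by staff on site and by video. Volunteered events are covered by the open questions. What remains is events that are both unseen and unvolunteered.

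**3. The plan's own figure.** Section 4.5 sets 20 participants, based on an earlier simulation study of 18 and on flight capacity. There is no formula to reproduce. The number fits the stated capacity: 6 scenarios per day × up to 4 sessions = 24. No adverse event rate or precision target is stated.

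**4. What would zero events in 20 show with full capture?** The one-sided 95% upper limit solves (1 − p)^20 = 0.05:

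p = 1 − 0.05^(1/20) = 1 − 0.8609 = 0.139, or 13.9%.

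**5. Illustration with incomplete capture.** Let d be the share of events that reach the record. The documents give no value, so the values of d below are assumptions. The recorded rate is p × d, so the limit on the true rate is 0.1391/d. If the true rate were 10% (also assumed), the chance of an empty record is (1 − 0.10 × d)^20.

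| Assumed d | Upper limit after 0/20 | Chance of an empty record at a true rate of 10% |
|---|---|---|
| 1 | 13.9% | 12% |
| 0.75 | 18.5% | 21% |
| 0.50 | 27.8% | 36% |
| 0.25 | 55.6% | 60% |

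The lower rows could apply, if at all, to minor or private events. They are not plausible for visible events when staff are watching one participant at a time.

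**The case against.** The strongest reply is that capture is far from haphazard. Staff attend, one is ready to step in, recordings and field-notes are reviewed, and feedback is examined after each session. The opening and closing questions give each participant a chance to mention a problem. The study plans no participant adverse event rate, and its safety objective concerns the drone flights. With 20 participants, even perfect capture leaves a limit of 13.9%. For a manikin simulation, awareness-based recording is a defensible choice.

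Most of this stands, and it narrows the point to minor, unseen and unvolunteered events. It does not remove the point: observation does not reveal what a participant conceals, and an open question permits a report without asking for one.

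Three stronger readings are tempting, and the documents do not support them:

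- **That an empty record would be uninterpretable.** It remains informative about visible events on site.
- **That work package 1 has the same gap.** Section 3.6 uses the same recording rule, but the interview topic guide and the content of the Appendix 1 flowchart are not shown, so nobody can say from the document that interviewees are not asked. Section 3.6 also gives the interviewer a procedure for wellbeing concerns.
- **That distressed participants would go without support.** Section 4.8 places sources of help in the Participant Information Sheet, which does not depend on an event being reported.

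Reporting detail could be left to a statistical analysis plan that is not shown. The wording of the participant instruments is fixed in the protocol, however, and an analysis plan cannot recover answers to a question that was not put.

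**Conclusion.** The point holds for work package 2 in a limited form. Recording depends on awareness, distress is foreseen, and neither printed instrument directly asks about harm. Visible or volunteered events should be caught; for minor or undisclosed ones, a record of no events is weak evidence.

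The firm figure is the 13.9% upper limit for 0/20. It assumes full capture, all 20 participants taking part and independent participants. The limits of 18.5%, 27.8% and 55.6% rest on assumed capture shares and should not be read as estimates for this study. Asking everyone would not make 20 participants more precise than the 13.9% limit; it would reduce the avoidable uncertainty about whether events went unmentioned.

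This is a cheap improvement to data capture. It is neither a contradiction in the protocol nor a threat to its planned timing and usability summaries.

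**What to change.** Add one fixed question to Appendix 3, for example: *Did you have any injury, physical discomfort or distress during the simulation?* Put it to every work package 2 participant, including those who stop early. State that last part explicitly, because section 4.5 lists inability to finish through distress among the exclusions and the Appendix 2 introduction presumes that the AED was retrieved. Report the number asked and the number with any event.

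The cost is one question in a conversation already planned at up to 5 minutes, plus one line of reporting. The small downside is that more minor events will be logged. A question asked straight after the run will not pick up effects that appear later, and the report should say so.

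If the question is not added, the report should state that adverse events were recorded without direct questioning of participants.
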